## **Research Protocol Lung Institute Dallas**

from the participants will contribute to building an awareness of the phenomena. Awareness of the patient, empathy, active listening, and providing comfort to the participants will be used (Smith et al., 2009).

Yardley's second broad principle is *commitment*. Commitment comes from the degree of attentiveness to the participant during the interview, the thoughtfulness of the work, and the completeness of the analysis undertaken. As described, the analysis needs to be conducted systematically and also be sufficiently interpretative- rather than simply describing, the analysis must also be interpretive and reflective. The third broad principle is *transparency* and how clearly the stages of the study are presented to the reader. This principle suggests a careful description of how the participants were selected, how the interview was conducted and the steps used to analyze the data. Also the study must provide cohesiveness, and the themes need to mesh together logically. With this, the foundational steps of the IPA method need to be clearly demonstrated (Smith et al., 2009). In this study, each stage of the study will be defined in the presentation of data. This will allow another researcher to replicate the study if desired.

Yardley's fourth principle, *impact and importance*, relates to the study's ability to tell the researcher something interesting, important or useful" (Smith et al., 2009). This study will inform the public and medical community on the safety and efficacy of autologous stem cell treatment for chronic lung disease.

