## 6. STUDY DESIGN

This study uses a concurrent mixed-methods approach to collect and analyze both qualitative and quantitative data. The *quantitative* arm will use a non-experimental, descriptive approach to measure and analyze pre- and post-stem cell treatment pulmonary function test results of treated patients. Measurement of the occurrence of adverse events will also be part of the quantitative arm.

Pre-treatment pulmonary function test results (measured by FEV1) will be compared with a six-month post-treatment pulmonary function test result (FEV1) for each patient. The aim of this method is to generalize an improvement in pulmonary function (measured by FEV1) among the general population of all individuals treated by autologous cell therapy for chronic lung disease.

The *qualitative* arm of the study uses an interpretive phenomenological approach to collect and analyze pre- and post- cell therapy anecdotal data regarding perceived quality of life among treated patients. Phenomenological research involves investigating the lived experience.

Qualitative research has several assumptions (D. Nicholls, 2009; Ritchie & Lewis, 2003). Primarily, there is no predetermined theoretical framework- rather the theory, if any, is derived from the data. Secondly, qualitative research is context-driven. Finally, qualitative researchers focus on the *emic* perspective that concerns itself with the view, perspectives and descriptions of others.

This study uses an *interpretive phenomenological analysis* (IPA) approach throughout the study from planning to data collection to analysis. This methodology is used to illuminate each participant's variation of the same general phenomenon (in this case, COPD) (Reissman, 2008; Ritchie & Lewis, 2003).

Data from both arms of the study will be combined following data collection for analysis, discussion and presentation. Safety data on adverse outcomes will be tracked and reported separately as a descriptive, quantitative analysis.

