#### **11c. Measurement tools used**

Pulmonary function test (FEV1)

Quality of life questionnaire (*see attached*)

Rev\_2/5/16 Page 6 of 10

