## **H. FOLLOW-UPS**

1. LI CONDUCTS A FOLLOW-UP EVALUATION VIA A TELEPHONE CALL AT 2 WEEKS.
  - a) TWO CALL ATTEMPTS ARE MADE.
2. LI CONDUCTS AN ADDITIONAL FOLLOW UP PHONE CALL CONDUCTED AT 12 WEEKS.
  - a) TWO CALL ATTEMPTS ARE MADE.
3. PATIENT IS ADVISED TO RETURN TO CLINIC AT 6 MONTHS FOR EVALUATION, LABS, PULMONARY FUNCTION, PULSE OXIMETRY AND SIX MINUTE WALK TEST.
  - a) IF RETURN TO CLINIC IS NOT POSSIBLE DUE TO DISTANCE, THE PATIENT IS ADVISED TO GO TO A LOCAL PHYSICIAN FOR EXAMINATION, LABS, PULMONARY FUNCTION, PULSE OXIMETRY, AND SIX-MINUTE WALK TEST AT 6 MONTHS.
  - b) TWO CALL ATTEMPTS ARE MADE TO OBTAIN PATIENT PROGRESS VIA A QUALITY OF LIFE SURVEY.

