**PATIENT CHECK-IN**

2. Is today the first treatment day for the Patient?
- **If NO** > Skip to Step 5 of this SOP
  - **If YES** > Proceed to Step 3 of this SOP

3. Office Manager receives Patient and processes paperwork and completes Patient Flow Chart as required.
- Has Office Manager reviewed and collected the required registration paperwork below, as well as assists the Patient with any remaining paperwork required for processing?
    - ✓ New Patient Packet (If NPP completed via Portal; OM must obtain hard copies of forms e and f)
      - a) Personal Information;
      - b) Emergency Contact Information;
      - c) Referral Source;
      - d) Medical History;
      - e) Authorization to Verbally Discuss Health Information;
      - f) Patient Bill of Rights;
      - g) How to File a Complaint; and
    - ✓ Provided the Patient with LI Privacy and Security Practices Notice
    - ✓ Consent Form Review and Completion; and
    - ✓ Quality of Life Survey
- **If NO** > Must complete this Step prior to moving forward.
  - **If YES** > Proceed to Step 4 of this SOP

10Mar2016 - version 2.0

LI-001

4. Office Manager processes payment.
- Has Office Manager collected and processed payment by completing the following?:
    - ✓ Obtaining a signed Payment Agreement;
    - ✓ Providing invoice and copy of payment agreement to Patient; and
    - ✓ Note payment in required systems (both EMR and CRM)
- **If NO** > Must complete this Step prior to moving forward.
  - **If YES** > Proceed to Step 5 of this SOP

5.	
Office Manager updates EMR as required.
 
 
• Has Office Manager scanned any required paperwork (e.g.: Registration, Payment Agreement) into the EMR chart; and
 
• Completed the following EMR steps? 
 
✓ Patient Check-In
 
✓ Exam Room
 
 
 
 
➤ If NO > Must complete this Step prior to moving forward.
 
➤ If YES > Proceed to Step 6 of this SOP

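### The promised before-and-after phenomenological analysis has no specified source of pre-treatment accounts; only a check-in survey covers quality of life at baseline

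*Combined protocol and SAP*

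**What the plan says.** Section 6 states that the qualitative arm will "collect and analyze pre- and post- cell therapy anecdotal data regarding perceived quality of life among treated patients". It adds that interpretive phenomenological analysis is the "approach throughout the study from planning to data collection to analysis", so the method is meant to govern what is collected as well as how it is read.

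Section 12b names the Clinical COPD Questionnaire as the instrument for this arm and describes the analysis as a search for themes that recur across patients' anecdotes. It then summarises published principles for judging qualitative work. Two of them refer to an interview: one values the "degree of attentiveness to the participant during the interview", and another asks for a careful account of "how the interview was conducted and the steps used to analyze the data".

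On data collection, section 11c lists two tools: the FEV1 test and a "Quality of life questionnaire", described as attached. Section 11 provides follow-up at 2 weeks, 3 months and 6 months, in clinic or by telephone, and a patient journal kept from discharge. Policy CL-005, section H, says of the six-month contact that "TWO CALL ATTEMPTS ARE MADE TO OBTAIN PATIENT PROGRESS VIA A QUALITY OF LIFE SURVEY". The Office Manager SOP, Step 3, lists a "Quality of Life Survey" among the items collected at check-in on the first treatment day.

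**The concern.** A before-and-after analysis of lived experience needs an account from each side of treatment. The plan describes ways for patients to give accounts afterwards, but none beforehand.

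The gap matters more here than in a controlled trial. Section 2a says there are no control groups and section 11b says nobody is blinded, so the patient's own earlier state is the only comparator. Section 5c expects patients to report improvement, and section 14 says they pay for the treatment. If the pre-treatment state is not recorded in the patient's words, a narrative theme of improvement depends on how patients remember it weeks or months later. Section 12b says the study will inform the public and the medical community about efficacy. A missing baseline account cannot be recovered once treatment has been given.

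**Working it through.** The plan gives no figure to reproduce on this point. The check is to list every source that could feed the qualitative arm, with its timing and form, and to see whether any passage assigns it to the analysis.

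| Source | Where | Timing | Form | Assigned to the qualitative analysis? |
|---|---|---|---|---|
| Quality of life survey | Office Manager SOP, Steps 2–3 | Before treatment, first day only | Survey; content not visible | Not named in sections 6, 11 or 12b as a baseline |
| Chief complaint | Venous SOP Step 12; Bone Marrow SOP Step 10 | Before infusion | Clinical record | No |
| History and review of systems | Venous SOP Step 14; Bone Marrow SOP Step 12 | Before infusion | Clinical record | No |
| Practitioner's history and examination or progress note | Venous SOP Step 18; Bone Marrow SOP Step 15 | Before infusion | Clinical record | No |
| Patient journal | Section 11 | From discharge | Patient's own notes, used as a recall aid | Indirectly, through follow-up |
| Contacts at 2 weeks and 3 months | Section 11; CL-005 section H | After treatment | Visit or call, form not specified | Collect quality of life |
| Contact at 6 months | Section 11; CL-005 section H | After treatment | Visit or call; survey | Collects quality of life |
| Research interview | Not scheduled or described | – | – | – |

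Counts from the table:

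- Research interviews specified: 0 before treatment, 0 after.
- Quality-of-life surveys specified before treatment: 1, at check-in.
- Free-form accounts explicitly scheduled before treatment for the research: 0.
- Possible free-form sources after treatment: the journal and three contacts.

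So two comparisons must be kept apart. Survey answers at check-in can be set against survey answers at six months; the documents support that. Narrative accounts before treatment cannot be set against narrative accounts after it, because no procedure names the first half.

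Cost of asking open questions at the four existing points (check-in, 2 weeks, 3 months, 6 months), with 200 patients from section 12a:

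- Hours = patients × contacts × minutes ÷ 60.
- Each minute costs 200 × 4 ÷ 60 = 13.3 hours.
- At an assumed 5 minutes: 200 × 4 × 5 ÷ 60 = 66.7 hours.
- At half that time (2.5 minutes): 33.3 hours. At double (10 minutes): 133.3 hours.

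These figures assume that every patient is reached at every contact. They exclude coding and analysis of up to 200 × 4 = 800 short accounts.

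**The case against.** The strongest reply has four parts.

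- **A baseline does exist.** The check-in survey is required on the first treatment day, before the patient passes to clinical staff. This stands. A reader might infer that no quality of life is collected before treatment, or that no before-and-after comparison is possible. The Office Manager SOP contradicts both.
- **Other pre-treatment notes exist.** Chief complaint, history and examination notes are recorded before infusion, and the researcher is also the primary clinician. This is true, so the survey is not the only pre-treatment record of any kind. But these are clinical records, and no passage assigns them to the qualitative analysis.
- **The interview is mentioned only in general principles.** Both mentions in section 12b paraphrase published criteria and do not set a procedure. This also stands: reliance on an interview is a fair inference and not an explicit commitment. The baseline gap does not depend on it, because it follows from section 6 set against section 11, CL-005 section H and the check-in step.
- **The questionnaire may contain open items.** It is attached to the protocol but is not in the available text, and section 12b moves from the instrument straight to anecdotes. Open items cannot be ruled out. A reader might conclude that none of the 200 patients would have a pre-treatment account; the documents do not support that as a fact. If open items exist, the remaining fault is that no passage names them as the baseline source.

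The follow-up contacts could also serve as conversational interviews. That would help the post-treatment side only.

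**Conclusion.** The concern holds in a limited form. The plan promises a phenomenological analysis of accounts from before and after treatment, specifies no research interview, and names no source for the pre-treatment accounts. Its one pre-treatment quality-of-life collection is a survey at check-in, which supports a comparison of survey answers but not, as described, a comparison of narratives. Themes of improvement drawn from the narratives would rest on recall, in an uncontrolled, unblinded study of self-paying patients.

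The conclusion assumes that the attached questionnaire either has no open items or is not meant as the narrative baseline, and that the pre-infusion clinical notes are not meant for this analysis. If either was intended, saying so would close most of the gap. It should be settled before patients are treated, because baseline accounts cannot be collected afterwards.

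**What to change.** **Preferred.** In section 11c, add a few open, non-leading questions, or name the existing open items in the attached questionnaire. Ask them in the same words alongside the check-in survey before the first treatment and at each existing follow-up contact. Record the answers verbatim, and state in sections 6 and 12b that these answers are the source for the phenomenological analysis. Keeping the questions few and open respects section 6's position that theory should come from the data.

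The cost is a short question guide, a few minutes per contact (about 67 hours in all under the 5-minute assumption; about 33 to 133 hours if the time is halved or doubled), and coding time, which may well be the larger part. No new visits are needed.

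**Alternative.** Limit sections 6 and 12b to a before-and-after comparison of questionnaire answers with post-treatment comments, and drop the pre-post claim about lived experience. This costs only wording.

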### 13. RISK AND BENEFIT ANALYSIS

All measures are taken to minimize or mitigate risks to the patient. The following lists the potential risks as indicated on the patient informed consent:

- **Adverse reaction to stem cells** - There is a possibility of an adverse reaction to the application of stem cells. This risk is minimized by using autologous (your own) unaltered stem cells.
- **Anemia** - There have been reports of anemia with harvesting of stem cells from the circulation. This risk is low. To minimize this risk we request blood work (CBC).
- **Embolus development** - An embolus is a clot that may be from blood or cells such as fat or bone marrow. There is a chance that an embolus or emboli (plural) may develop with stem cell procedures. This risk is low and is minimized due to our stem cells processing protocols.
- **Failure of the procedure** - There is a chance that undergoing stem cell application will not alleviate symptoms, resolve inflammation, or assist in regenerating tissue.
- **Fever** - Fever associated with stem cell harvesting usually responds to acetaminophen. If fevers persist, a work-up for infection must be completed.
- **Infection** - Infection may occur at the donor site where the bone marrow or fat was harvested or at the IV site and recipient site of application. To minimize risk infection prevention protocols are maintained and followed during the treatment process and patient education is provided on post treatment cleaning and wound care.
- **Pain** - Any procedure can result in pain. To minimize this risk we ask that our patients communicate any discomfort so that we can reduce or mitigate.
- **Numbness/tingling** – Although a low risk, this has been reported with leukapheresis (the process of separating stem cells from peripheral blood in the vein). Laboratory analysis may be required along with calcium infusion.
- **Respiratory difficulties** - Breathing difficulties (which are usually temporary) or post-operative pneumonia, may occur as a result of any procedure or surgery. Pulmonary embolus, a blood clot causing blockage of an artery in the lungs may occur as a result of any procedure or surgery. Pulmonary embolus may be fatal.
- **Stroke** - Though a low risk and unlikely, there is a possibility that a stroke will occur during the procedure or in the recovery period.
- **Transfers of undiagnosed cancer** – There is a risk that undiagnosed cancer in the area where the stem cells are harvested may be transferred to the recipients area of transplantation. To minimize risks, stem cells will not be altered in any way, thereby reducing the risk of tumor induction by carcinogens.

Rev\_2/5/16 Page 8 of 10

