**3. RULE OUTS FOR *BONE MARROW* PROCEDURE**

- a) CURRENT BLOOD THINNER FOR ANY TYPE OF EXISTING HEART CONDITION;
- b) OSTEOPOROSIS;
- c) BILATERAL HIP REPLACEMENT;
- d) RADIATION OF PELVIS AREA (INCLUDING PROSTATE SEED IMPLANTS)
- e) ACTIVE TUBERCULOSIS;
- f) HISTORY OF CANCER (WITHIN THE PAST 5 YEARS);
  - i. ON A CASE-BY-CASE BASIS, PROVIDER MAY APPROVE PROCEDURE(S) FOR NON-AGGRESSIVE/NON-ACTIVE CASE.

- g) IDENTIFICATION OF NEW NODULES/MASSES PER CHEST X-RAY/CT SCAN REPORT THAT HAVE NOT BEEN NOTED AS STABLE.
  - i. DOCUMENTATION OF STABILITY MUST BE RECEIVED FOR CONFIRMATION PRIOR TO TREATMENT.
- h) ACTIVE INFECTION (PULMONARY OR OTHER);
- i) A HISTORY OF RECENT HOSPITALIZATION (REQUIRING MECHANICAL VENTILATION IN A PERIOD OF ONE MONTH BEFORE TREATMENT);
- j) END STAGE KIDNEY FAILURE;

10Mar2016 - version 2.0

LI-001

- k) ACUTE HEART FAILURE;
- l) UNCONTROLLED DIABETES;
- m) OTHER CONDITION(S) THE PROVIDER OR PRINCIPAL INVESTIGATOR FEELS WOULD INTERFERE WITH TREATMENT PROTOCOLS; AND/OR
- n) MEDICATION RULE-OUTS AS FOLLOWS:
  - i. MUST BE OFF ANTICOAGULATION DRUGS AND OTHER MEDICATIONS AND/OR SUBSTANCES THAT CAUSE BLEEDING. (MUST BE HELD FOR AN ALLOTTED TIME WITH PRIOR APPROVAL FROM PCP/PRESCRIBING PHYSICIAN-SPECIFIC HOLD TIMES ARE SUBJECT TO MEDICATION/SUBSTANCE TYPE.)
  - ii. METHOTREXATE (IF UNABLE TO HOLD FOR 1 WEEK PRIOR TO TREATMENT)

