
14.
	
Clinic Staff completed initial evaluation, including medical history.
 
 
• Has Clinic Staff completed the following Patient History? 
 
✓ Patient Complaint/Primary Reason for Visit
 
✓ Social;
 
✓ Medical;
 
✓ Allergies;
 
✓ Medications;
 
✓ Surgical;
 
✓ Family; and
 
✓ Review of Systems
 
 
 
 
➤ If NO > Step must be completed prior to proceeding.
 
➤ If YES > Proceed to Step 15 of this SOP

15.	
Clinic Staff draws blood and affixes IV line to catheter.
 
 
• Has Clinic Staff completed the following? 
 
✓ IV site is prepped and disinfected;
 
✓ Affix tourniquet to upper arm;
 
✓ Insert IV catheter into desired site;
 
✓ Remove needle from catheter;
 
✓ Affix Harvest PRP kit 60ml syringe to catheter and draw approximately 55ml of blood;
 
✓ Remove syringe and affix IV drip line to catheter;
 
✓ Wrap with Coban bandage to hold catheter in place;
 
✓ Check the patency and flow to make sure it is correct;
 
✓ Once correct, close off IV drip line until reinfusion; and
 
✓ Dispose of supplies in designated biohazard/sharps containers.
 
 
 
 
➤ If NO > Step must be completed prior to proceeding.
 
➤ If YES > Proceed to Step 17 of this SOP

16.	
Clinic Staff draws blood and affixes IV line to catheter.
 
 
• Has Clinic Staff completed the following? 
 
✓ IV site is prepped and disinfected;
 
✓ Affix tourniquet to upper arm;
 
✓ Insert IV catheter into desired site;
 
✓ Remove needle from catheter;
 
✓ Affix Harvest PRP kit 35ml syringe to catheter and draw approximately 30ml of blood;
 
✓ Remove syringe and affix IV drip line to catheter;
 
✓ Wrap with Coban bandage to hold catheter in place;
 
✓ Check the patency and flow to make sure it is correct;
 
✓ Once correct, close off IV drip line until reinfusion; and
 
✓ Dispose of supplies in designated biohazard/sharps containers.
 
 
 
 
➤ If NO > Step must be completed prior to proceeding.
 
➤ If YES > Proceed to Step 17 of this SOP

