21.	
Clinic Staff conducts on-going oversight of Patient during administration.
 
 
• Has Clinic Staff confirmed the patency and flow are correct?
 
 
➤ If NO > Step must be completed prior to proceeding.
 
➤ If YES > Proceed to Step 22 of this SOP

22.	
Clinic Staff starts nebulizer treatment.
 
 
• Has Clinic Staff completed the following? 
 
✓ Place glutathione and saline into nebulizer medicine cup and provide Patient with instructions to begin nebulizing treatment; and
 
 
 
 
➤ If NO > Step must be completed prior to proceeding.
 
➤ If YES > Proceed to Step 23 of this SOP

10Mar2016 - version 2.0

LI-001

23.	
Clinic Staff discontinues IV line and nebulizer; and provide post care instructions.
 
 
• Has the Clinic Staff completed the following? 
 
✓ Turn off nebulizer when treatment completed;
 
✓ When final product has emptied IV bag, use normal saline flush to flush entire contents of IV line;
 
✓ Remove IV catheter;
 
✓ Place 2x2 gauze pad over site, affix coban bandage;
 
✓ Instruct Patient to remove gauze and coban after 20 to 30 minutes; and
 
✓ Dispose of supplies in designated biohazard containers.
 
 
 
 
➤ If NO > Step must be completed prior to proceeding.
 
➤ If YES > Proceed to Step 24 of this SOP

-----	---

24.	
Has Clinic Staff provides Patient with discharge folder and post-care instructions and answered any Patient questions or concerns?
 
 
• Has Clinic Staff advised the Patient of the below post-care instructions and ensured that they understand said instructions; answering any questions or concerns? 
 
✓ Briefly review and explain the discharge folder contents to Patient;
 
✓ Review LI follow-up procedures; and
 
✓ Review Patient Journals for quality of life outcome data.
 
 
 
 
➤ If NO > Step must be completed prior to proceeding.  ➤ If YES > Proceed to Step 25 of this SOP

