
18.
	
Practitioner and an additional member of Clinic Staff (minimum of 2) will conduct and document on the Medical Record a “Time-Out”.
 
 
• Has the procedure team conducted pre-op verification check-point with an alert and aware Patient? 
 
✓ Patient Name
 
✓ DOB (Date of Birth)
 
✓ Procedure Type
 
✓ Allergies
 
✓ Anesthesia
 
✓ Procedure Site/Side & Process
 
 
 
 
➤ If NO > Time-Out must be completed and documented prior to proceeding.
 
➤ If YES > Proceed to Step 19 of this SOP

19.
	
Clinic Staff administers prophylactic antibiotic injection.
 
 
• Has Clinic Staff administered Rocephin? 
 
✓ Inject Rocephin 1g IM (Intra Muscular) via gluteus maximus; or
 
✓ In event of Penicillin (PCN) allergy, administer Lincocin 600mg IM via gluteus maximus.
 
 
 
 
➤ If NO > Step must be completed prior to proceeding.
 
➤ If YES > Proceed to Step 20 of this SOP

20.
	
Practitioner instructs Patient on safety protocol.
 
 
• Has Practitioner instructed Patient of lateral decubitus positioning? 
 
✓ Patient is placed on right or left side-lying position depending on patient preference; if applicable.
 
 
 
 
➤ If NO > Instruct Patient on safety protocol prior to proceeding.
 
➤ If YES > Proceed to Step 21 of this SOP

21.	
Has Practitioner checked on Patient readiness in the procedure room and noted Start-Time of Procedure once ready to commence procedure?
 
 
• Patient Readiness 
 
✓ Is Patient comfortable?
 
✓ Does Patient need anything?
 
✓ If Applicable, do we have Patient preferred music playing?
 
✓ If Applicable, is their O on?
 
 
 
• Start-Time 
 
✓ Note the Start-Time of Procedure
 
 
 
 
➤ If NO > Step must be completed prior to proceeding.
 
➤ If YES > Proceed to Step 22 of this SOP

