**PLEASE NOTE:**

- ***The CRRF must be received by the due date printed on your form to allow sufficient time for our IRB panels to review your study for continuing review approval before your initial or most recent approval expires.***
- ***If the CRRF is not received and reviewed before the study's approval expiration date, your study's approval will have expired, barring continuation of the study until a new approval is issued.***
- ***Continuing research after expiration of IRB approval is a violation of federal law.***
- ***Missed CRRF submission deadlines are the sole responsibility of the Sponsor and/or designee regardless of whether or not the IRB notifies you.***

You are obligated to notify MaGil IRB of the following occurrences:

[figure not shown]
- Any and all amendments or changes to the protocol, investigator guide, or consent/assent scripts (all changes must receive IRB approval before implementation).
- Any and all changes to the protocol that are implemented without prior IRB approval to eliminate an apparent immediate hazard to subjects – *must be reported within 24 business hours of implementation*
- Related (Possible, Probable or Likely) Serious Adverse Events and unexpected and related Adverse Events – *must be reported within 5 business days from the date of discovery*
- Significant Protocol Deviations/Violations – *must be reported within 5 business days from the date of discovery*
- Unanticipated Problems involving risks to subjects or others – *within 5 business days of discovery*
- All materials used to recruit study subjects – *these items must receive IRB approval before being used*
- Any and all changes in the research activity

The Principle Investigator (PI) is bared from making any changes in research, without prior approval of MaGil IRB, except when it is necessary to eliminate immediate risk to study subjects. In addition, it is the responsibility of the

PI to uphold the following three ethical principles outlined in the Belmont Report throughout the entire conduct of this study:

- **Respect for Persons** – individuals should be treated as autonomous agents, and persons with diminished autonomy are entitled to protection.
- **Beneficence** – maximize possible benefits and minimize possible harms.
- **Justice** – benefits and burdens of research should be distributed equally.

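### The section 13 risk list does not match the SOPs: it cites leukapheresis, which none of them performs, and omits bleeding and reactions to the agents used

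*Combined protocol and SAP*

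**What the plan says.** Section 13 of the protocol introduces its list with "The following lists the potential risks as indicated on the patient informed consent". Thirteen risks follow. The numbness/tingling entry states that "this has been reported with leukapheresis (the process of separating stem cells from peripheral blood in the vein", and adds that laboratory analysis and a calcium infusion may be needed.

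The SOPs describe a different collection. On the first treatment day, Venous Procedure SOP step 15 reads "Affix Harvest PRP kit 60ml syringe to catheter and draw approximately 55ml of blood". On later days, step 16 reads "Affix Harvest PRP kit 35ml syringe to catheter and draw approximately 30ml of blood". The Bone Marrow Aspirate SOP (step 13) draws about 60 ml, also by syringe. The blood is then spun in a processing cup.

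The SOPs also introduce several agents. Step 19 of the marrow SOP reads "Inject Rocephin 1g IM (Intra Muscular) via gluteus maximus", with Lincocin as the alternative in penicillin allergy. Step 22 of the venous SOP reads "Place glutathione and saline into nebulizer medicine cup and provide Patient with instructions to begin nebulizing treatment".

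Bleeding is recognized elsewhere. The CL-005 rule-outs for the marrow procedure state "MUST BE OFF ANTICOAGULATION DRUGS AND OTHER MEDICATIONS AND/OR SUBSTANCES THAT CAUSE BLEEDING", and section 9b of the protocol has the same rule. Section C.3 of CL-005 requires that the recognized risks and complications be explained to the patient.

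**The concern.** A risk list should follow from what is done to the patient. This one attributes a risk to a collection method that the SOPs do not use. It is also silent on harms that the same documents screen for before treatment. If the consent form carries the list as section 13 says, patients agree to an incision, a trocar through bone and several drugs without bleeding or drug reaction being named. That would fall short of the sponsor's own rule in CL-005 section C.3. Safety is research question 1, so the stated risks should at least describe the treatment under study.

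**Working it through.** No arithmetic beyond counting applies. The check sets the section 13 list against each collection step and each agent in the SOPs.

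**1. The list.** The 13 items are reaction to stem cells, anemia, embolus, failure of the procedure, fever, infection, pain, numbness/tingling, respiratory difficulties, stroke, transfer of undiagnosed cancer, incorrect cells, and unintended differentiation.

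**2. Leukapheresis.** Four SOPs are present: venous, bone marrow, discharge and office manager. The draws are about 55 ml and 30 ml (venous SOP, steps 15 and 16), 30 ml (discharge SOP, step 8) and 60 ml (marrow SOP, step 13). All are by syringe through an IV catheter, followed by centrifugation. Leukapheresis is performed in 0 of 4 SOPs, and none lists calcium among its supplies.

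**3. Omitted items, by procedure.**

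| Item | Marrow | Venous | Where in the SOPs | In section 13? |
|---|---|---|---|---|
| Bleeding or hematoma | Yes: scalpel, trocar, IV site | Yes: IV site | Marrow 13, 26–30; venous 15–16 | No |
| Reaction to antibiotic | Yes | No | Marrow 19 | No |
| Reaction to bupivacaine | Yes | No | Marrow 25 | No |
| Reaction to heparin | Yes: catheter flush, instrument wash | No | Marrow 13, 22 | No |
| Reaction to ACD-A | Yes: processing | Yes: processing | Marrow 4, 22; venous 4, 7 | No |
| Reaction to glutathione | No | Yes | Venous 22; discharge 12 | No |
| **Missing** | **5** | **3** | | **0 of 6 listed** |

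The discharge SOP gives glutathione only on its venous branch; step 4 sends other patients past it to step 15. The Introduction mentions glutathione in general terms, but the marrow SOP has no such step.

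**4. Nearby entries do not cover the gap.** The only reaction entry is confined to stem cells. Anemia is attributed to harvesting cells from the circulation, and breathing difficulty to a procedure or surgery. None of these names blood loss at a site or a drug reaction.

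**5. The plan recognizes both kinds of harm.** Step 2 of the venous and marrow SOPs checks bleeding tendencies and screens for antibiotic and anesthetic allergy, with substitutes. The same step sends patients on blood thinners to the venous procedure only, so bleeding is not solely a marrow question. The marrow Time-Out (step 18) confirms allergies and anesthesia.

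**The case against.** Four objections deserve a hearing.

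- **The consent form was not available for this review.** Section 13 says its risks are those on the consent, not that they are everything on it. CL-005 sections C.3 and E.3 separately require that patients be informed of the risks. This stands: a reader might infer that patients were not told about bleeding, but the documents show only that section 13 does not list it.
- **The leukapheresis wording says where numbness has been seen.** It does not tell patients that they will undergo leukapheresis, and its gloss loosely resembles drawing and spinning blood. This stands in part. The wording is misleading next to these SOPs, but deleting the entry would remove the only numbness/tingling item.
- **Bleeding and allergy are managed operationally** through the checks, the medication holds, and pressure on the incision site. True, but screening does not replace disclosure.
- **The reporting standard is not shown to be wrong.** The IRB notice requires reports of "Related (Possible, Probable or Likely) Serious Adverse Events and unexpected and related Adverse Events", and a reader might infer that a faulty list corrupts the judgement of what is unexpected. No passage makes section 13 the reference; the term is simply undefined. If section 13 were used, omitted bleeding or drug reactions would count as unexpected, giving more reports. Related serious events are reportable either way. Only numbness/tingling could move in the other direction, and only on that same assumption.

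**Conclusion.** The mismatch holds as a point of consistency and disclosure. One listed risk is tied to a procedure found in none of the four SOPs. Six relevant risks are absent from a list of 13: five apply to marrow patients and three to venous patients, with bleeding and ACD-A common to both.

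Two further inferences should be resisted. The first is that safety counts will come out wrong. Section 6 plans a separate descriptive report of adverse outcomes, and section 5b hypothesizes no adverse events at all, so any event counts whether listed or not. The second is that all six omissions apply to every marrow patient; glutathione does not appear in the marrow SOP.

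The conclusion rests on the SOPs present in the documents. Section 11 also names an adipose SOP, which is absent from the text and from the CL-005 attachment list. The ACD-A item assumes that some of it remains in the infused product, which the documents do not quantify. No FEV1 or safety result depends on this point, but it bears directly on what patients are told and should be put right.

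**What to change.** 1. Reconcile section 13 with the SOPs in force, step by step, and check the consent text against the result. If the consent carries the same list, amend both together.
2. Add bleeding or hematoma at the harvest and IV sites, and reactions to the agents used. Arrange these by procedure, so that marrow patients see the antibiotic, bupivacaine, heparin and ACD-A, and venous patients see ACD-A and glutathione.
3. Correct the leukapheresis wording. If numbness/tingling applies to something the SOPs do use, attribute it to that; do not simply delete the entry.

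The cost is a revision of the protocol (and of the consent where needed), one IRB amendment, and a longer risk list for patients to read.
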